Although the ultimate goal of using WATs should be increased MVPA, such data was not reported in previous studies on older people. Moreover, the suggested additional measures for facilitating the adoption of WATs by older people have not previously been tested. It is worth testing the efficacy of a combined intervention of exercise training plus WAT intervention in which BCTs have been incorporated. Little is presently known about the efficacy of using a WAT intervention among older people with frailty. The main hypothesis is that the WAT intervention plus exercise training programme will increase physical activity levels compared to an exercise programme alone. If we are successful in proving the hypothesis, we will propose studying the long-term effects (i.e., increased daily MVPA and the adoption of a physically active lifestyle) of this intervention in the main study with a larger sample size with a longer follow-up period.

B. Research plan and methodology (Appendix 1: Consort Research Flowchart)

Aim: A single-blinded, repeated-measures, two-arm pilot cluster RCT is proposed to examine the feasibility and preliminary effects of an exercise programme with or without a WAT intervention for promoting physical activity levels among community-dwelling older people with frailty. To explore the acceptability of the WAT intervention, a focus group with all participants in the experimental group (4-6 people per group) will be interviewed by JS (the Co-I).

Subjects and Settings: A district community health centre will be viewed as one unit/cluster. Eligibility criteria for district community health centres are those that are funded by the Hong Kong (HK) government and under the supervision of the Social and Welfare Department of HK, and thus that meet a specific set of standard regulations and criteria on environment and practices. Six community centres, which provide similar types of community care and social support services for community-dwelling older people, will be invited by a convenience method to work as collaborators in this study. The target population of this study are community-dwelling older people with frailty who will be recruited through the community centres.

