The Control Condition: The same physical training and BCTs support will be arranged for the control group.

Instruments and Measures:

Participants will be assessed on a variety of outcomes (described below) at 1 week and at 1 and 3 months (T1 – T3) after the programme, which will be compared with the baseline assessment (T0). The participants will be asked to wear an ActiGraph Wgt3x accelerometer on their non-dominant wrist for 7 days before the commencement of any intervention, as well as during each outcome assessment time point.

Socio-demographic data: The following data will be collected: 1) data on age, gender, marital status, exercise habits, living conditions, and level of education, 2) the participants' health-related information, including their morbidities, cognitive status, medications, and number of hospital and out-patient clinic visits in the past 12 months.

Feasibility:

To understand the feasibility of this intervention, the frequency with which the participants in the experimental group use the tracker over the time of the study (i.e., 112 days), the recruitment rate, the attrition rate, the participants' adherence to the exercise regimen, and reports of adverse effects will be monitored.

Primary outcome measurement: Activity levels

The participants' physical activities and sedentary time will be objectively measured using a ActiGraph wGT3X accelerometer.

Secondary outcome measurements

Fitbit Data (only participants in the experimental group): The total steps per week, total walking distance per week, and time spent in different heart rate zones (50-69%, 70-84%, and >85% of the maximum heart rate) of an individual will be collected.

Physical Endurance: This will be evaluated using different physical tests:

1. The participants' lower-limb muscle and upper-limb strength will be assessed using a 30-second chair stand test and a handheld Jamar Hydraulic Hand Dynamometer, respectively.
2. Mobility will be assessed through the Timed-up-and-Go (TUG) test and by their gait speed (2-m walk). These two tests assess the overall performance of the lower limbs and walking speed, which can reflect the effect of exercise in enhancing the participants' overall physical endurance.

Exercise Self-efficacy: The participants' self-confidence in their ability to exercise in a variety of circumstances (e.g., even when they were feeling tired) will be assessed using the Chinese Self-Efficacy for Exercise scale (CSEE).

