Official Title: Enhancing physical activity levels of community-dwelling older people with frailty through an exercise intervention with or without a wearable activity tracker (WAT)-based intervention: a feasibility and pilot study

Date of the document: 22/03/2018

Approved by the Human Subjects Ethics Sub-committee of The Hong Kong Polytechnic University on 13/04/2018

Statistical Analysis:

SPSS version 23.0 will be used to analyse the data. Descriptive statistics will be generated for the demographic data and feasibility tests. The baseline characteristics of the participants in the two groups from the six community centres will be compared using unpaired t test for the continuous variables, a chi-square test for the categorical variables, and the Mann-Whitney U test for the ordinal variables. Normality assumptions for the variables will be examined by a K-S test. The group attendance and drop-out rate of the participants in the study groups will be reported. An intention-to-treat analysis will be adopted. An independent sample Student's t-test or Mann-Whitney U test will be used to examine differences between the control and experimental groups in the outcome variables. For categorical and dichotomous outcome variables, an χ^2 test will be used to test differences between the groups. If significant differences between the groups at baseline have been identified, these data will be treated as covariates and adjusted for as needed. A p-value of < 0.05 will be considered statistically significant. ANOVA will be used to measure the effectiveness of the intervention. If the data were non-normal, Friedman's test will be used instead. Post-hoc within-group comparisons will be done using paired t-tests or Wilcoxon's signed rank test, and Bonferroni adjustments will be made.

Content analysis will be used to analyse the interview data. All audio-taped interviews will be transcribed into Cantonese by the RA and the transcriptions will be checked for accuracy by two members of the research team before the analysis.

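### Intention-to-treat is promised with no method for missing outcomes, so the ANOVA or Friedman effectiveness step would rest on completers unless data are imputed

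*SAP*

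**What the plan says.** All analysis text is in the SAP, Statistical Analysis. It commits to a population: "An intention-to-treat analysis will be adopted". It then names the effectiveness step: "ANOVA will be used to measure the effectiveness of the intervention". The fallback follows: "If the data were non-normal, Friedman's test will be used instead". Post-hoc comparisons are paired, within-group tests with a Bonferroni adjustment. Separately, it says: "An independent sample Student's t-test or Mann-Whitney U test will be used to examine differences between the control and experimental groups in the outcome variables". The software is SPSS 23.0. Attendance and dropout by group are to be reported.

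The Protocol (section B, Aim) describes the design: "A single-blinded, repeated-measures, two-arm pilot cluster RCT is proposed". Under Instruments and Measures, outcomes are taken at baseline (T0) and at three times after the programme (T1 to T3), with seven days of accelerometer wear at each. Under Sample size and Procedures, baseline is completed before the centres are randomised.

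Neither document defines the intention-to-treat set. Neither mentions imputation, carry-forward, a mixed model, generalised estimating equations or a sensitivity analysis for missing outcomes.

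**The concern.** An intention-to-treat promise has two parts: participants are analysed in the arm they were allocated to, and those with incomplete data are not silently removed. The SAP gives no means of delivering the second part. The methods named for effectiveness work on complete sets of visits. A participant seen at T1 and T2 but not at T3 would leave a four-visit analysis altogether, and the T1 and T2 data would go too.

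Two things are at stake. First, information is discarded in a pilot of 60 whose size is justified by estimating an effect size. Second, completers are selected after allocation. If the reasons for missing a visit are tied to activity and differ between arms, the contrast carried forward to the main study could be distorted. The primary outcome is more exposed than most, because a failed week of accelerometer wear creates a gap even when the participant attends.

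**Working it through.** **1. Is the ANOVA a repeated-measures one?** The SAP says only ANOVA, so this is an inference. Four features support it:
- The design is described as a "repeated-measures, two-arm pilot cluster RCT".
- There are four assessments per participant.
- The substitute is Friedman's test, which is for related samples and is not the counterpart of a between-group ANOVA.
- The post-hoc tests are paired.

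**2. Which participants does each named method use if nothing is imputed?**

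| Method in the SAP | Participants used |
|---|---|
| Repeated-measures ANOVA (standard SPSS procedure) | those with every analysed visit |
| Friedman's test | those with every analysed visit |
| Independent t-test or Mann-Whitney, by visit | all seen at that visit |
| Paired t-test or Wilcoxon | those with both visits of the pair |

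None of these retains every randomised participant. The first two lose the most.

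**3. How many would be lost?** There is no plan figure to reproduce, because the documents give no missing-data rate for this trial. The inputs are N = 60 (Protocol, Sample size), three visits after allocation (T1 to T3), and 7.1% attrition among 85 in the earlier pilot (Protocol, Background).

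- *All loss is permanent dropout at 7.1%:* 60 × 0.071 = 4.3 lost, about 56 remain.
- *Each post-programme visit missed independently with probability m (assumed):* completers = 60 × (1 − m)³.

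| m | (1 − m)³ | Deleted | Remaining of 60 | Present at any one visit |
|---|---|---|---|---|
| 3% | 0.913 | 9% | 54.8 | 58.2 |
| 5% | 0.857 | 14% | 51.4 | 57.0 |
| 7.1% | 0.802 | 20% | 48.1 | 55.7 |
| 10% | 0.729 | 27% | 43.7 | 54.0 |

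The last column shows how much smaller the loss is for a visit-wise t-test. Independent misses give more deletion than permanent dropout at the same rate: at 7.1%, about 12 lost against about 4.

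**4. What does a likelihood-based model keep?** In one simulated data set of 60 with four visits and 7.1% missing at each post-programme visit, 51 participants were complete. A linear mixed model fitted to all visits used all 60 participants and 229 of 240 observations.

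**5. Evidence from the earlier pilot.** It allocated 85 people to three groups and reports F(2,76) for attendance. The error degrees of freedom imply 76 + 3 = 79 analysed. Attrition of 7.1% implies 85 × 0.929 = 79.0. The two agree, which is consistent with dropouts having been left out of that test. It does not show what will be done here.

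**6. Bias, as an illustration only.** Assume no true effect, correlation 0.7 between visits, and logistic dropout after T1 that depends on T1 activity.
- Same mechanism in both arms: bias in the completer T3 difference is about zero.
- Control arm only, 7.1% dropout, log-odds slope 0.5 to 1.0 per SD: about −0.02 to −0.05 SD.
- Control arm only, 8% to 21% dropout, slope 1.0: about −0.05 to −0.13 SD.

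For scale, the standard error of a difference with 30 per arm is √(2/30) = 0.26 SD before any allowance for clustering.

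**The case against.** The strongest reply is that this is silence, not contradiction. The SAP never says incomplete cases will be dropped, and imputation before the ANOVA would satisfy both the intention-to-treat sentence and the named test. That stands, and it is why the conclusion is conditional. But the SAP specifies no imputation, and the default behaviour of the named methods is deletion.

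Several stronger readings are tempting and are not supported:
- *The SAP names a repeated-measures ANOVA.* It does not; that is a well-supported inference.
- *Every reported result would be a completer result.* Visit-wise t-tests and Mann-Whitney tests lose only those absent at that visit.
- *Four visits can each be missed after allocation.* Baseline precedes randomisation, so the exponent for post-allocation loss is three. Baseline accelerometer failures could add to the loss, but no rate is given.
- *A known bias follows.* The figures above need an assumed mechanism that differs between arms. Poor tracker engagement, an obvious candidate reason for loss, can arise only in the experimental arm, so even the direction is open.

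It can also be said that this is a feasibility pilot, that attrition is itself a feasibility measure, and that dropout will be reported by group. Loss would therefore be visible. Reporting it does not restore the discarded data or define the analysis set.

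**Conclusion.** The point holds in conditional form. Carried out as written and without imputation, the effectiveness step would rest on participants with no missed visit, which does not deliver the intention-to-treat analysis the SAP promises. This rests on reading ANOVA as repeated-measures and on standard SPSS handling.

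The size is uncertain. It runs from about 4 of 60 lost, if the earlier pilot's attrition recurs and is all permanent dropout, to about 16 of 60 if visits are missed independently at an assumed 10%. Bias may be negligible or a fraction of a standard error, depending on a mechanism the documents do not describe. The case for change does not need a particular rate: the plan lacks a rule, and a better method is available in the named software.

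**What to change.** In the SAP, for continuous outcomes:
- Replace the ANOVA/Friedman step with one between-arm linear mixed model (SPSS MIXED) using all available visits, with arm, visit, arm-by-visit and baseline value. Include effects for participant and for centre, since centres are the randomised unit, and use small-sample degrees of freedom because there are only six centres.
- Define the intention-to-treat set: every participant analysed in the arm of their centre. State how many have no post-programme measurement, because a model with baseline as a covariate gains no outcome information from them.
- For clearly non-normal outcomes, use a transformation or a suitable generalised mixed model rather than Friedman's test.
- Keep the completer analysis as a sensitivity check.

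A stated imputation rule before the existing ANOVA would also close the missing-data gap, but it would leave the centre effect unaddressed.

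The cost is SAP wording and slightly more analysis work in software already named; no new data are needed. The downside is reliance on data being missing at random given what is in the model, which the SAP should state.

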Sample size: Teare et al., 2014 recommended that a pilot study is required a total number of participants between 60 and 100 when estimating the effect size for a continuous outcome. Thus, sixty participants will be recruited from six community centres. We estimate that about 25-50% of the members of these centres will be eligible to participate (Schultz-Larsen et al., 2007; Liu, 2017). We will target moderate to large centres with the total number of centre members around 800. Given that we can screen 200 older people (50 in each centre) per 4 to 6 weeks, and based on our previous study in similar centres (Liu et al., 2017), we believe that we will need about 3 to 4 months to recruit 60 participants (with 30 subjects recruited per 4 to 6 weeks in two-three centres) for this study. Given the difficulty of obtaining details of the backgrounds of all potential participants in these community settings, a properly random sample cannot be implemented. Thus, convenience sampling will be used to recruit participants among the collaborative community centres. Using computer-generated random numbers, a biostatistician not affiliated with this study will randomize the centres in a 1:1 ratio into either: the control or the experimental groups. Participants from each centre will be placed in their centre's corresponding group to avoid 'contamination' effects across participants. To avoid selection biases, the allocation to the study groups will be concealed from the researchers until sample recruitment and baseline measurements have been completed. Appendices 1 and 2 show the CONSORT research flow chart and the timeline of this study.

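### Six centres are randomised, but the SAP's between-arm tests treat the 60 participants as independent, so p < 0.05 is too lenient if outcomes are correlated within centre

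*SAP*

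**What the plan says.** Protocol section B describes a two-arm pilot cluster trial. Under Subjects and Settings: "A district community health centre will be viewed as one unit/cluster". Under Sample size, "a biostatistician not affiliated with this study will randomize the centres in a 1:1 ratio", and every participant takes the allocation of his or her centre; Procedures repeats this. The size is given as "Thus, sixty participants will be recruited from six community centres", taken from a cited recommendation of 60 to 100 for pilot studies. No power, precision, ICC or design effect accompanies it. Recruitment is described "with 30 subjects recruited per 4 to 6 weeks in two-three centres", so centre sizes may differ.

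The between-arm hypothesis stands at the end of Protocol section A: "The main hypothesis is that the WAT intervention plus exercise training programme will increase physical activity levels compared to an exercise programme alone". The same paragraph makes a larger main study conditional on success.

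The SAP (Statistical Analysis) sets significance at p < 0.05 and plans:

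- for outcome variables, a "t-test or Mann-Whitney U test will be used to examine differences between the control and experimental groups in the outcome variables";
- for categorical and dichotomous outcomes, a chi-square "test will be used to test differences between the groups";
- in addition, "ANOVA will be used to measure the effectiveness of the intervention", with no factors named.

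The SAP mentions the six centres only for the baseline comparison, which also uses participant-level tests. The only ICC in either document concerns rater reliability (Protocol, Intervention fidelity and RA training).

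**The concern.** The t-test, Mann-Whitney and chi-square tests take their standard errors from variation between participants and assume that participants are independent. Under centre randomisation, the arm difference also carries the variation between three centres and three other centres. If that variation is above zero, the planned tests understate the standard error, and a chance difference between centres can be reported as a tracker effect.

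Nothing else in the SAP repairs this. Covariate adjustment is limited to variables that differ significantly at baseline, which does not model the remaining correlation within centres. The Bonferroni correction covers only post-hoc within-group comparisons.

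At stake is every between-arm outcome test, including the primary activity outcome, and the effect estimate that would inform the main study.

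**Working it through.** **Inputs.** From the documents: 6 centres, 1:1, so 3 v 3; 60 participants, so a mean of m = 10 per centre; alpha 0.05 (sidedness not stated, two-sided assumed). Not in the documents and therefore assumed: ICC from 0 to 0.10; total outcome variance 1; for the unequal case, centres of 5, 10 and 15 in each arm.

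**The plan's own figure.** The 60 comes from a cited range and has no formula inputs, so it can be neither reproduced nor refuted. 6 × 10 = 60 is only an arithmetic check. The nominal 5% is recovered at ICC 0.

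**Step 1: design effect.** DE = 1 + (m − 1) × ICC = 1 + 9 × ICC; effective n = 60/DE.

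- ICC 0.01: DE 1.09, effective n 55.0
- ICC 0.05: DE 1.45, effective n 41.4
- ICC 0.10: DE 1.90, effective n 31.6

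**Step 2: type I error by approximation.** Error ≈ 2 × (1 − Φ(1.96/√DE)).

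- ICC 0.01: 1.96/1.044 = 1.877, error 6.1% (6.05% before rounding)
- ICC 0.05: 1.96/1.204 = 1.628, error 10.4%
- ICC 0.10: 1.96/1.378 = 1.422, error 15.5%

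**Step 3: type I error by simulation.** Null trials with a normal centre effect, at least 100,000 per setting (20,000 for Mann-Whitney). The chi-square uses beta-binomial data at 50% prevalence without continuity correction. Repeat runs agree to within about half a percentage point.

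| Test at nominal 5% | ICC 0.01 | ICC 0.05 | ICC 0.10 |
|---|---|---|---|
| t-test, centres of 10 | 6.1% | 10.5% | 15.6–15.9% |
| t-test, centres of 5/10/15 | 6.3% | 11.4% | 17.6% |
| Mann-Whitney, centres of 10 | 5.5% | 9.7% | 14.9% |
| Chi-square, centres of 10 | 6.2% | 10.8% | 16.3% |
| t-test on six centre means (4 df), centres of 10 | 4.9% | 5.1% | 4.9% |

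The centre-mean test gives about 4.4 to 4.9% with unequal centres. Regressing the outcome on baseline first, without an arm term, and averaging the residuals by centre gives 4.4 to 5.2% with equal and unequal centres.

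**Step 4: price in precision.** 95% half-width in outcome SDs on centre means = 2.776 × √(2 × (ICC + (1 − ICC)/10)/3).

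- ICC 0: 0.72
- ICC 0.01: 0.75
- ICC 0.05: 0.86
- ICC 0.10: 0.99

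Ignoring clustering, it is 2.002 × √(2/30) = 0.52.

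**The case against.** **It is only a pilot, and the ICC may be negligible.** The aim is feasibility and preliminary effects. The centres are described as similar and one trainer runs all sessions, both of which push the ICC down. At ICC 0.01 the error is only about 6%, and at zero the planned tests are nominal. This limits the consequence and stands as a caveat. But participants train in groups of at most 10 within their own centre, which pushes the ICC up, and nothing in the documents supports assuming zero. Six centres cannot show it either: at a true ICC of 0.05, the centre variance is estimated as zero in 37% of simulated trials. The plan still applies p < 0.05 and ties the main study to proving the hypothesis.

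**The ANOVA may behave differently.** If it is a group-by-time analysis, stable centre differences cancel and only centre variation in change matters. With an assumed within-person correlation of 0.6 and a cross-sectional ICC of 0.05, a change-score test has error of about 5% if centre effects are fully stable, about 8% if 80% stable and about 12% if 50% stable. So the rates in the table apply to the t-test, Mann-Whitney and chi-square, not to the ANOVA. The ANOVA escapes inflation only in the fully stable case, and as written it has no centre term.

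**A valid analysis has little power with 3 v 3 centres.** For a true effect of 0.5 SD, the centre-mean test has power of about 32%, 30%, 24% and 19% at ICC 0, 0.01, 0.05 and 0.10, against 48% for the participant-level test at ICC 0. This is true and should be stated openly. It reflects the design and does not justify a test with the wrong error rate.

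**Conclusion.** The concern holds: the analysis does not match the unit of randomisation, and no other section corrects it. The inflation is conditional on a positive ICC, for which the documents give no value. It is small at 0.01, about double the nominal 5% at 0.05 and about three times at 0.10, and somewhat larger if centre sizes differ. No stated figure is refuted, because the 60 carries no power or precision claim, but it was applied to a clustered design without a design effect. The defect reaches every participant-level between-arm test, including the primary outcome, and should be corrected before any comparison of the arms, since a method chosen after seeing centre results would carry little weight.

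**What to change.** Replace the participant-level between-arm tests in the SAP with one pre-specified analysis that respects the centre.

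- **Simplest choice:** regress each outcome on its baseline value without an arm term, average the residuals by centre, and compare the six centre means by t-test on 4 df. Compare centre proportions in the same way for categorical outcomes.
- **Alternative:** a linear mixed model in SPSS MIXED with a random centre effect, participants nested in centres and Satterthwaite degrees of freedom. In a balanced, single-time-point approximation its error was 3.0 to 4.9% over ICC 0 to 0.10. It was not tested with unequal centres or repeated measures, and the centre variance will often be estimated as zero.
- **Not suitable as a 5% test:** an exact permutation of centres, whose smallest two-sided p is 2/20 = 0.10.

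Report each effect with its 95% CI, and the ICC with its interval. Say that an ICC from six centres is very imprecise (at a true 0.05, 95% of estimates fall between 0 and 0.27) and must be combined with external values when the main study is sized. In the sample size text, state that 60 rests on a cited pilot recommendation and give the effective number over a range of assumed ICCs. Given the pilot aim, it would also be sensible to label between-arm p-values exploratory and to base the decision to proceed on feasibility and the effect estimate with its CI.

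The cost is a rewrite of the between-group part of the SAP, together with the wider intervals and lower power shown above.

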The Inclusion Criteria are: 1) community-dwelling older people aged ≥ 65 years; 2) able to communicate in Cantonese to ensure that they understand our instructions; 3) able to walk with or without an assistive device and able to complete the Time Up and Go (TUG) test with no specific cutoff point to ensure that their mobility and balance is good enough to join the exercise training; 4) able to use a smartphone; and 5) in a pre-frail or frail state as determined using the Fried Frailty Index^[1]; including: i) having experienced an unintentional loss of 10% of body weight in the past year; ii) exhaustion: by answering 'Yes' to either 'I felt that everything I did was an effort', or 'I could not get going in the last week'; iii) a slow walk time: with an average walking speed in the lowest quintile stratified by median body height; iv) reduced grip strength: with maximal grip strength in the lowest quintile stratified by the body mass index quartile; and v) a Physical Activity Scale for Elderly-Chinese (PASE-C) score in the lowest quartile (i.e., < 30 for men and < 27.7 for women). The presence of 1-2 indicates pre-frailty, ≥ 3 items indicates frailty.

The Exclusion Criteria are older people who: 1) have any physical conditions that hamper their performance of the exercise programme or use of the WAT, such as visual or hearing problems. 2) regularly engage in moderately intense exercise (such as hiking, Tai Chi) for ≥ 3 hours per week.

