Frailty status: This will be assessed based on Fried's frailty five phenotypes as mentioned in the sample inclusion criteria. **Physical activity level** is one criterion of frailty that will be assessed using the 10-item PASE-C to measure self-reported occupational, household, and leisure activities for the last week.

Self-reported sedentary behavioral and physical activity: This will be assessed using the Global Physical Activity Questionnaire-Chinese version (C-GPAQ), which comprises 16 questions designed to estimate an individual's self-perceived level of physical activity in three domains (occupational, transport-related and discretionary or leisure time).

Motivation to engage in physical activity: This will be assessed by the 19-item Chinese version of the Behavioral Regulation in Exercise Questionnaire-2 (C-BREQ-2). The C-BREQ-2 is a 19-item questionnaire assessing five dimensions: amotivation, external regulation, introjected regulation, identified regulation, and intrinsic regulation. Each item is rated on a 5-point scale ranging from 0 = "not true for me" to 4 = "very true for me", with higher scores indicative of higher motivation.

Procedures: Ethical and access approval will be obtained from the Ethics Review Committee of The University and study venues, respectively. Potential participants will be referred to the research team by the community centres. An RA will screen all potential participants for their eligibility to participate in this study. Written informed consent will then be obtained from all of the participants, to whom all aspects of the study will be explained and questions answered. They will then be interviewed to obtain their demographic data, and baseline assessment. After that, the participating community centres will be randomized to either the control or experimental group. Participants from each centre will be placed into their centre's corresponding group to avoid 'contamination' effects across participants. At 1 week, 1 month, and 3 months post-intervention, an independent assessor who is blinded to the group allocations will assess the participants' outcomes, which will be compared with the baseline assessment. Another RA will collect all "Fitbit activity-related data" from the participants in the experimental group every week. All of the participants in the experimental group will be invited to attend the focus group interviews, which will be conducted by JS after the first post-test T1 and T3.

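### The SAP names no test for frailty status; the chi-square it most naturally falls under ignores the order of the states and cannot adjust for frailty at entry.

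*SAP*

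**What the plan says.** **Outcome.** The Protocol (Instruments and Measures, Frailty status) lists frailty among the secondary outcomes and bases it on Fried's "frailty five phenotypes as mentioned in the sample inclusion criteria". Criterion 5 of the Inclusion Criteria admits only pre-frail or frail people and gives the cut-points: "The presence of 1-2 indicates pre-frailty", and three or more items mean frail. The Background names robust as the remaining state, which implies a count of zero. The Protocol does not say whether the outcome is the three-level state or the 0 to 5 count.

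**Tests.** The SAP's Statistical Analysis section separates three kinds of variable at baseline and uses "the Mann-Whitney U test for the ordinal variables". For outcomes it offers a t-test or Mann-Whitney test in general. A rule opening "For categorical and dichotomous outcome variables" then prescribes chi-square. No ordinal class is named for outcomes, and frailty is not mentioned. ANOVA, or Friedman's test for non-normal data, is also listed for effectiveness.

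**Adjustment.** Baseline data become covariates only where the groups differ significantly at baseline. On significance the SAP says: "A p-value of < 0.05 will be considered statistically significant".

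**Size.** The Protocol's Sample size section says: "Thus, sixty participants will be recruited from six community centres". The reason given is that "a pilot study is required a total number of participants between 60 and 100 when estimating the effect size for a continuous outcome". A biostatistician outside the study "will randomize the centres in a 1:1 ratio".

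**The concern.** Among the outcomes compared between arms, frailty status is the only one that the Protocol itself defines in categories; the others are accelerometer measures, physical test results and questionnaire scores. If the chi-square sentence does not cover frailty, it has almost nothing to cover.

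A chi-square test on a two-by-three table treats the three states as unordered. A move from frail to pre-frail and a move the other way count only as departures from equal proportions. The test also takes no account of where a person began, although nobody begins robust and the starting state limits where a person is likely to finish. It returns neither a direction nor an effect estimate, yet estimating an effect is the stated reason for the sample size.

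The conditional covariate rule does not repair this. With about 30 per arm, a sizeable imbalance in entry frailty can be non-significant and so go unadjusted. If the rule is triggered, chi-square has no place for a covariate, and the SAP names no adjusted method for a categorical outcome.

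**Working it through.** **No figure to reproduce.** The plan states no power for any outcome. Its 60 participants are the lower end of the cited 60 to 100 range.

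**Inputs from the documents**
- 60 participants, six centres, 1:1 by centre: 60/2 = 30 per arm and 60/6 = 10 per centre if centres are equal.
- Significance level 0.05; sidedness is not stated, so two-sided is assumed.
- Attrition of 7.1% in the earlier pilot described in the Background: 60 × (1 − 0.071) = 55.7, or about 28 per arm.
- Entry state pre-frail or frail only.

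**Inputs that are assumptions**
- Frail share at entry: 10%, 20%, 35% or 50%.
- Link between entry state and later state: weak, moderate or strong.
- Common odds ratio within entry state: 2, 3, 4 or 6.

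These give 4 × 3 × 4 = 48 scenarios, each with 1,500 simulated trials of 30 per arm and independent participants. The simulation error of one power near 50% is √(0.5 × 0.5/1,500), about 1.3 points.

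**Power.** Three tests were compared on the three states: Pearson chi-square; Mann-Whitney, which uses order; and the van Elteren stratified Wilcoxon test, which uses order and entry state. Selected results (gains computed before rounding):

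| Frail at entry | Link | Odds ratio | Chi-square | Mann-Whitney | Stratified | Gain, order | Gain, order and entry state |
|---|---|---|---|---|---|---|---|
| 10% | strong | 2 | 13.5% | 17.5% | 19.0% | 3.9 | 5.5 |
| 20% | strong | 2 | 14.1% | 16.1% | 21.0% | 2.0 | 6.9 |
| 10% | moderate | 4 | 58.1% | 69.5% | 72.5% | 11.4 | 14.4 |
| 35% | moderate | 4 | 51.0% | 62.3% | 72.9% | 11.3 | 21.9 |
| 50% | moderate | 4 | 50.1% | 62.0% | 74.5% | 11.9 | 24.4 |
| 50% | strong | 4 | 44.5% | 53.6% | 72.1% | 9.1 | 27.6 |

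Over all 48 scenarios, order alone is worth 2.0 to 11.9 points. Order with entry state is worth 5.5 to 27.6 points, median about 14, and reaches 18 or more in 12 scenarios.

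**Check on the order component.** With the same noncentrality, the largest loss from testing on 2 rather than 1 degree of freedom is 10.5 points. It occurs at noncentrality 5.2, where the 1-df test has 62.6% power. This agrees with the simulated upper end of about 12, allowing for simulation error.

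**Second model.** Five items were driven by one latent severity, with entry at one or more items, 30 independent participants per arm and 3,000 trials per setting.
- Larger shift: chi-square 56.4%, Mann-Whitney on the states 67.7%, Mann-Whitney on the count 70.3%, baseline-adjusted count 76.9%. The total gain is 76.9 − 56.4 = 20.5 points.
- Smaller shift: 27.7%, 37.5%, 39.8% and 45.7%. The total gain is 45.7 − 27.7 = 18.0 points.

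Both totals lie inside the range above.

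**Expected counts.** With equal arms, the expected count is the arm size times the pooled share of the state. It is below 5 when the share is below 5/30 = 16.7%, or 5/28 = 17.9% after attrition. At 30 per arm:
- 20/60/20% gives 6, 18 and 6: no small cell.
- 10/70/20% gives 3, 21 and 6: two of six cells small.
- 10/80/10% gives 3, 24 and 3: four of six cells small.

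In the 48 scenarios, 4% to 41% of cells were below 5. The usual rule (at most 20% of cells below 5) failed in 13% to 99% of tables, and in more than half of the tables in 32 of 48 scenarios.

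**The case against.** The strongest reply is that the SAP never assigns frailty to chi-square. It allows Mann-Whitney for outcomes and uses it for ordinal variables at baseline, so an analyst could treat frailty as ordinal, or score it as a count. This stands in part: chi-square is the most natural reading, not an explicit assignment. The Mann-Whitney reading removes the loss from order but still omits routine adjustment for the T0 value. Leaving the choice open also lets it be made after the data are seen.

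Four stronger readings are tempting, and the documents do not support them.
- A reader might infer a loss of about 20 points. That depends on rates and effects that the documents do not give, and it bundles order with baseline adjustment.
- A reader might infer that most expected counts are too small. In no scenario were most cells below 5, and some plausible splits have no small cell.
- A reader might infer that chi-square inflates false positives. With no treatment effect, the second model gave it a type I error of 4.1%.
- A reader might infer that the plan never adjusts for baseline. It does, conditionally.

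It is also fair that the primary outcome is accelerometer-measured activity, that the passages on reversing frailty are background, and that no power is claimed for any outcome. This limits the priority. Finally, neither simulation models clustering, so the powers and the type I error need not hold under centre randomisation.

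**Conclusion.** The point holds in a limited form. The SAP does not say how frailty status is scored or tested. Its most natural rule discards the order of the states and leaves entry frailty out unless a significance test brings it in. The cost is about 2 to 12 points of power for order alone, and about 5 to 28 points (median about 14) for order and entry state together. These figures assume 30 per arm, two-sided testing at 0.05, the frail shares, transition patterns and odds ratios listed, and independent participants. They illustrate the cost and are not properties of this trial. Sparse cells are likely but depend on how participants spread across the three states. Because this is a secondary outcome in a pilot, it is an inexpensive improvement of low to moderate priority.

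**What to change.** In the SAP:
- State whether frailty is scored as the 0 to 5 count or as the three states, and analyse it as an ordered outcome.
- Always adjust for the T0 value, whatever the baseline significance test shows.
- Fit this within whatever model accounts for centre.
- Report the three-state table by arm and baseline state descriptively.
- If a test of that table is kept, use a trend or exact test.

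The cost is SAP wording; the five items are already collected at each assessment. The downside is that a model coefficient is less familiar to readers than a table of percentages, which the descriptive table largely offsets.
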